6.1.4 Receiving, Storage, Dispensing and Return

6.1.4.1 Receipt of Investigational Product

Dex4® will ship the investigational product to the research offices in the Women and Babies department at Sunnybrook Health Sciences Centre and the Dex4® tablets will be stored at room temperature. The Dex4® tablets do not require any special handling.

Upon receipt of the investigational product and/or study supplies, an inventory will be performed and a receipt log filled out and signed by the research team member accepting the shipment. The designated study staff will count and verify that the shipment contains all the items noted in the shipment inventory. Any damaged or unusable product in a given shipment will be documented in the study files. The study sponsor will be notified of any damaged or unusable product that was supplied to the site.

6.1.4.2 Storage and Stability

The Dex4® tablets will be stored in the bottles that they were shipped in at room temperature as per the product monograph. The investigational product will be reconciled by the research team at regular intervals, in addition to reconciliations performed during monitoring. Reconciliation will include verification of investigational product kit/device assignment, inventory and dispensing documentation.

6.1.4.3 Dispensing of Investigational Product

21 tablets will be dispensed to each participant; After the fasting blood glucose is drawn they will be instructed to consume the tablets and no more than 300ml of water within 5 min.

6.1.4.4 Return and/or Destruction of Investigational Product

At the completion of the study, there will be a final reconciliation of investigational product shipped, used, and remaining. This reconciliation will be documented. Any discrepancies noted will be investigated, resolved, and documented prior to return or destruction of unused investigational product. Documentation of investigational product destroyed on site will be retained in the study files.

6.1.5 Participant Compliance Monitoring and Assessment

The participants will be observed taking the IP by the research staff and will not need to take the IP home or administer it on an ongoing basis. Participants who do not/are not able to take all 21 tablets or who vomit the tablets within 120 minutes will not be included in the primary outcome assessment. However, data regarding side effects will be retained for the secondary outcomes.

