2.1 Background

Gestational diabetes mellitus (GDM) is defined as any degree of hyperglycemia with onset or first recognition during pregnancy (5-6). Up to 70% of women with GDM will develop type 2 diabetes mellitus (T2DM) during their lifetime (3). Diabetes Canada and the Society of Obstetricians and Gynecologists of Canada recommend that pregnant women be screened for GDM between 24-28 weeks of pregnancy (7,8). The current 2-step approach for GDM detection involves a screening test and a diagnostic test, both of which use a liquid glucose challenge. In Canada, most pregnant women routinely undergo screening for GDM by consuming 50g of a liquid glucose solution and having a blood test for serum glucose after 1 hr, this test is commonly known as the 50g glucose challenge test (50g GCT). Women with a positive screening test (serum glucose 7.9 to 11.0 mmol/L) take a second test to confirm the diagnosis. For the second test, called a 2 hour oral glucose tolerance test (OGTT), women fast for 8 hours and then consume 75g of glucose beverage, and serum glucose levels are taken at fasting, 1 and 2 hours after drinking the glucose beverage. The 75g OGTT is the gold standard and is performed for GDM diagnosis.

Unfortunately, up to 30% of women do not tolerate glucose beverage (9-11). Side effects include: nausea, vomiting, bloating, abdominal pain, diarrhea, sweating and headache which may prevent them from completing testing for GDM (9-11). If women cannot complete screening, the diagnosis of GDM may be missed, increasing the risk of complications for mothers and their babies, such as a larger baby and trauma during delivery. Women who have had a history of GDM are at higher risk of developing cardiometabolic complications such as lipid abnormalities, hypertension and hyperinsulinemia (5, 15). GDM also carries a risk for later development of T2DM to the mother and fetus (2, 3). Unfortunately, GDM prevalence has doubled in the past 10 years in all ethnic populations and reaches 25-32% in some (16-19), with an estimated 19% of cases proceeding on to become T2DM within the first 9 years after pregnancy (2). Because of T2DM's long asymptomatic phase, many women will have already developed health complications by the time they are diagnosed. A missed diagnosis of GDM is a missed opportunity to intervene and offer prevention for T2DM.

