4 STUDY DESIGN

4.1 General Design

Our project is a population-based, prospective randomized crossover study. Women who fall into the screen positive group of the 50g GCT (1 hour serum glucose of 7.8-11 mmol/L) will be offered participation in the study. 28 Participants will be recruited and will be randomly assigned using a pre-populated allocation table to take either the standard OGTT test (75g of glucose beverage) first or the alternative OGTT test (21 Dex4® tablets) first. The first test will be referred to as OGTT-1 and the second test will be referred to as OGTT-2. After completing OGTT-1 at the first test appointment, a questionnaire about pregnancy, health, diet and exercise habits, and side effects from the first test will be completed by the participant (Questionnaire A). After completing OGTT-2 at their second test appointment, a questionnaire about side effects from the second test and test preference will be completed by the participant (Questionnaire B). Each woman will complete both tests within one week and each subject will serve as their own control. Results will be kept blinded in the case report forms until both OGTT tests are done. Serum glucose will be measured using the same internationally standardised glucose-oxidase method (RocheDiagnosis) in the Sunnybrook Biochemistry lab. After serum glucose measurement, all results will be sent to the research team but only the standard of care glucose beverage test data will appear in electronic (or classical) medical records and be used for GDM diagnosis.

The following data will be collected by questionnaire at the first OGTT appointment:

- Estimated date of delivery
- # of previous pregnancies
- Previous diagnosis of GDM
- Pre-pregnancy weight (kg);
- Height (cm);
- Ethnic group (Caucasian, Indigenous, Hispanic, South Asian, East Asian, African, Middle Eastern, Other)
- History of macrosomic infant - ≥ 4000 g
- Polycystic ovary syndrome (yes-no);
- Medication (for corticosteroid use);
- First degree family history of T2DM
- Length of fast (hrs)
- Side effects (nausea, vomiting, headache, dizziness, sweating, other)

The following data will be collected by questionnaire at the second OGTT appointment:

- Side effects
- Preference for Dex4® or glucose beverage

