5.4 Participant Withdrawal and Discontinuation of IP

5.4.1 *Reasons for Withdrawal/Discontinuation of IP*

At their own discretion, participants may withdraw from the study at any time and for any reason. Study participants may also be withdrawn from the study at the discretion of the investigator for any of the following reasons:

- The investigator(s) decide(s) that continuing in this study would be harmful to the participant.
- The participant is unable or unwilling to follow the study procedures
- The pregnancy is terminated/lost

5.4.2 *Data Collection and Follow-up for Withdrawn Participants*

Participants withdrawing from the study will be contacted by the study research team requesting a final visit and to follow up with any unresolved adverse events. Once withdrawn from the study, no further study procedures or evaluations should be performed, or additional study data collected. However, every effort should be made to obtain permission to document the reason for withdrawal and to collect participant outcomes where possible. Any data collected prior to the withdrawal of consent may be retained and used by the sponsor.

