7.2 Study visits/Follow up

Screening Appointment: Eligibility will be confirmed and participants will sign the information and consent form.

Test Visit 1: OGTT-1 will be performed. Study staff will administer Questionnaire A for visit 1

Test Visit 2: OGTT-2 will be performed within 1 week of OGTT-1 study staff will administer Questionnaire B for visit 2

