7.4 Protocol Deviations

It is the responsibility of the investigator to ensure that only investigative procedures, as outlined in this protocol are performed on study participants; the occurrence of deviations from the protocol or SOPs are limited; and compliance with the regulations is maintained. Planned deviations from the protocol must not be implemented without prior agreement from the sponsor and approval from the local REB/ethics committee (EC), as required, unless to eliminate an immediate hazard to a participant.

Planned or unplanned deviations may occur on the part of the participant, the investigator, or study research team. In resolution to a deviation, corrective/preventative actions are to be developed and implemented in a timely manner. Protocol deviations will be documented and reported as required and assessed where necessary during analysis.

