11.2 Source Documents

Source data/documents are original documents, data and records in a clinical study that are necessary for the reconstruction and evaluation of the study. Examples of these original documents and data records include, but are not limited to:

- Worksheets
- hospital records
- medical records
- memorandum
- participants' diaries or evaluation checklists
- pharmacy dispensing records
- recorded data from automated instruments (i.e. ECGs)
- copies or transcriptions certified after verification as being accurate and complete
- participant files and records kept at the pharmacy
- entries entered directly into the printed CRF

The following data points will be recorded directly on the CRFs, and will be considered source data as no prior written or electronic record of data may be available:

The following data will be collected by questionnaire at the first OGTT appointment:

- Previous diagnosis of GDM
- Pre-pregnancy weight (kg);
- Height (cm);
- Ethnic group (Caucasian, Indigenous, Hispanic, South Asian, East Asian, African, Middle Eastern, Other)
- History of macrosomic infant - ≥ 4000 g
- Polycystic ovary syndrome (yes-no);
- First degree family history of T2DM
- Length of fast (hrs)
- Side effects (nausea, vomiting, headache, dizziness, sweating, other)

The following data will be collected by questionnaire at the second OGTT appointment:

- Side effects(nausea, vomiting, headache, dizziness, sweating, other)
- Preference for Dex4® or glucose beverage

Each participating site will maintain appropriate medical and research records for this study, in addition to regulatory and institutional requirements for the protection of confidentiality of participants. If electronic source data is printed it should be signed and dated by the investigator to confirm content and filed with other source documents.

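### The rule that removes failed glucose loads from the primary outcome covers the tablets only; stating it in the same terms for the beverage is a minor, cheap improvement

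*Protocol*

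**What the plan says.** **The rule.** On the primary outcome, Protocol section 6.1.5 states: "Participants who do not/are not able to take all 21 tablets or who vomit the tablets within 120 minutes will not be included". Their side-effect data are kept for the secondary outcomes. The same section adds: "The participants will be observed taking the IP by the research staff". Both statements concern the tablets.

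**The beverage.** Section 2.1 says that "up to 30% of women do not tolerate glucose beverage", names vomiting among the effects, and says the effects can stop women from completing testing. Section 6.1.3 allows the beverage test to be run in the hospital laboratory by phlebotomists. It states no check on intake and no consequence of a failed load.

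**What is recorded.** Side effects are asked about after both tests. For the second visit, section 4.1 says "a questionnaire about side effects from the second test and test preference will be completed by the participant"; for the first, section 7.2 says "Study staff will administer Questionnaire A for visit 1". Section 11.2 lists the items: "Side effects (nausea, vomiting, headache, dizziness, sweating, other"). Whether the load was fully taken is not a listed item for either test.

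**General provisions.** Section 5.4.1 lets the investigator withdraw a woman when "The participant is unable or unwilling to follow the study procedures". Section 7.4 says "Protocol deviations will be documented and reported as required and assessed where necessary during analysis".

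**The concern.** Each woman is her own control, so the primary comparison is a within-woman difference. A failed tablet load removes the pair. A failed beverage load that was still sampled meets no exclusion criterion, so its value can enter as the reference. If that value reads low because part of the load was lost, the tablet-minus-beverage difference for that woman is too high, and nothing on the tablet side offsets it.

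This goes beyond detail left to an analysis plan. The protocol does not leave evaluability open; it fixes a rule and fixes it for one test. A plan that follows section 6.1.5 inherits the asymmetry. The uncovered event is also one the protocol expects, since poor tolerance of the beverage is the reason for the trial.

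At stake is the mean difference at 1 and 2 hours. Fasting values precede the load and are unaffected. A test stopped before the blood draw gives no value and causes no shift.

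**Working it through.** **Inputs from the protocol.** 1-hour mean 10.6 mmol/L, SD 1.78 mmol/L, margin 20%, alpha 0.05, 28 women, 33% loss, 42 recruited (sections 10.2 and 10.4).

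**Inputs assumed.** Share p of analysed women with a failed but sampled beverage load: 5-10%. Shortfall D in those values: 1-2 mmol/L. Within-woman correlation r: 0.5, with 0 and 0.7 as alternatives.

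**The plan's own figures.** Margin = 0.20 × 10.6 = 2.12 mmol/L. Two one-sided tests for two independent groups, SD 1.78, true difference 0 and 0.05 per side give power 0.808 with 13 per group (26 in all) and 0.845 with 14 per group (28 in all). The stated 28 is thus reproduced to within two. Recruitment: 28 / (1 − 0.33) = 41.8, so 42.

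**Size of the shift.** Shift = p × D.
- 0.05 × 1 = 0.05 mmol/L; 0.05 / 2.12 = 2.4% of the margin
- 0.10 × 1 = 0.10 mmol/L; 4.7%
- 0.10 × 2 = 0.20 mmol/L; 9.4%

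Among 28 women, 5-10% is 28 × 0.05 = 1.4 to 28 × 0.10 = 2.8, that is, one to three women.

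**Effect on the chance of declaring equivalence.** Paired two one-sided tests, n = 28, 27 degrees of freedom, 0.05 per side. SD of the difference = 1.78 × √(2(1 − r)): 2.52 at r = 0, 1.78 at r = 0.5, 1.38 at r = 0.7.

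| r | True difference (tablets − beverage, mmol/L) | No shift | Shift +0.20 |
|---|---|---|---|
| 0.5 | 0 | >0.999 | >0.999 |
| 0.5 | +0.5 | 0.999 | 0.993 |
| 0.5 | +1.0 | 0.945 | 0.846 |
| 0.5 | +1.2 | 0.846 | 0.671 |
| 0.5 | −1.2 | 0.846 | 0.945 |
| 0 | 0 | 0.993 | 0.988 |
| 0 | +1.2 | 0.595 | 0.433 |
| 0.7 | +1.2 | 0.964 | 0.853 |

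At the low end of the assumed range (shift +0.05, r = 0.5), the figure at +1.2 falls only from 0.85 to 0.81.

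**Added spread.** Failed loads also add variance p(1 − p)D² = 0.10 × 0.90 × 2² = 0.36, so the SD rises from 1.78 to √(1.78² + 0.36) = 1.88. With the +0.20 shift, power stays above 0.999 at 0 and becomes 0.988 at +0.5, 0.630 at +1.2 and 0.924 at −1.2. The pattern is unchanged.

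**Is a difference of 1.2 expected?** The nominal tablet load is 21 × 3.64 = 76.44 g, and 76.44 / 75 = 1.019, about 2% above the beverage. Nothing in the protocol points to a true difference of that size.

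**Limits.** These figures are for 1 hour only. The Protocol Summary names the 2-hour value as primary, and no 2-hour mean or SD is given. Section 10.4 names a two-sample test; with 28 values per test treated as independent, its power at a true difference of 0 is 0.994, close to the r = 0 row.

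**The case against.** **Silence is not an instruction.** Section 6.1.5 sits under the heading for the investigational product, which explains why it names only tablets. It never says that failed beverage loads stay in. Elsewhere the comparator is a 75 g test, so an unfinished beverage can be treated as a deviation under section 7.4. This stands in part: retention is inferred from the absence of a criterion. But section 5.4.1 is discretionary and section 7.4 acts only where necessary; neither says what counts as a failed beverage load. The study treatment is not blinded, so a criterion chosen late could be chosen with the test and its values known.

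**Most of the data will exist.** Vomiting is asked about after both tests, so a vomited beverage could largely be identified. This stands. What remains is unfinished intake, which is not a listed item, and the missing statement of what to do with either event. No section says that beverage intake goes unobserved.

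**The harm needs several steps together.** The load must fail, the test continue, blood be drawn, the value read materially low, and the true difference lie near the margin. This stands and sets the importance.

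**Stronger readings the documents do not support.** A reader might take the 30% in section 2.1 as the share of failed beverage loads. With a 3 mmol/L shortfall that would give 0.30 × 3 = 0.90 mmol/L, 42% of the margin. But the 30% is an upper figure for intolerance of any kind, and the protocol says such effects may prevent completion, which gives missing values and no shift. A reader might also infer that the asymmetry favours the tablets. It does so only if tablets truly read lower; if they truly read higher, equivalence becomes harder to show.

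**Conclusion.** The asymmetry is real on the text: one test has a stated exclusion criterion for the primary outcome and the other has none. Its importance is minor. Under the assumed rates and shortfalls the 1-hour mean difference moves up by 0.05-0.20 mmol/L, and the equivalence conclusion is practically unchanged when the true difference is near 0. Only near the margin does it count. At r = 0.5 the chance of declaring equivalence falls from 0.85 to between 0.81 and 0.67 at a true difference of +1.2, and rises from 0.846 to 0.945 at −1.2 for the largest shift. The direction follows from failed loads reading low. The size rests on the assumed share, shortfall and correlation, none of which the documents give, and it is not established for the 2-hour value. A biased trial result cannot be inferred from this. What can be said is that a one-sided filter is avoidable at almost no cost.

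**What to change.** - In section 6.1.5, state the existing primary-analysis criterion in the same terms for both tests: a woman enters the primary comparison only if both loads were fully taken and neither was vomited within 120 minutes. This concerns the analysis set only and changes nothing in how either test is given.
- Record completeness of intake and any vomiting in the same way at both visits.
- Report the number of failed loads by test in the participant flow.
- Add a sensitivity analysis with all women who have measured values on both tests, whatever happened to the load.

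**Cost.** One sentence, one yes/no item on the case report form, one line in the participant flow and one extra analysis. A few pairs may be lost: 28 × 0.90 = 25.2, so about 25 remain if 10% fail. Even with zero within-woman correlation this lowers paired power at a true difference of 0 only from 0.993 to 0.985, and the plan already recruits 42 to obtain 28. The primary result would then describe women who tolerate both loads. The report should say so, and the sensitivity analysis and the counts by test show what that restriction leaves out.

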6.1.6 Prior and Concomitant Medications/Treatments

Participants may be on concomitant medications as appropriate to their pregnancy but these are not expected to interfere with the investigational product or standard glucose beverage.

Medications that will result in an exclusion from the study include: glucocorticoids (including betamethasone), terbutaline and metformin.

6.2 Behavioral Intervention(s) Description (if applicable)

During the time between the two OGTT tests, participants will be asked to refrain from drinking alcohol, and performing nonroutine exercise.

6.2.1 Administration of Intervention

Participants will be asked to ingest 21 Dex4® tablets and no more than 300ml of water within 5 minutes. Blood draws will be performed at fasting (before ingesting the dextrose monohydrate tablets), as well as 1 hour after (+/- 15 minutes) and 2 hours (+/- 15 minutes) after ingesting the dextrose monohydrate tablets.

7 STUDY SCHEDULE AND PROCEDURES

7.1 Screening

Women will have had to test positive on the 50g glucose challenge test, which would have already been part of their routine care.

7.2 Study visits/Follow up

Screening Appointment: Eligibility will be confirmed and participants will sign the information and consent form.

Test Visit 1: OGTT-1 will be performed. Study staff will administer Questionnaire A for visit 1

Test Visit 2: OGTT-2 will be performed within 1 week of OGTT-1 study staff will administer Questionnaire B for visit 2

7.3 Early Termination Visit

If the participant discontinues their participation in the study, the information about the participant and blood samples that were collected before they left the study may still be used. No new information will be collected (and no further testing of the blood sample will be done) without the participant's approval.

The Principal Investigator will keep any personal information about the participants in a secure and confidential location for 25 years and then destroy it according to Sunnybrook policy.

7.4 Protocol Deviations

It is the responsibility of the investigator to ensure that only investigative procedures, as outlined in this protocol are performed on study participants; the occurrence of deviations from the protocol or SOPs are limited; and compliance with the regulations is maintained. Planned deviations from the protocol must not be implemented without prior agreement from the sponsor and approval from the local REB/ethics committee (EC), as required, unless to eliminate an immediate hazard to a participant.

Planned or unplanned deviations may occur on the part of the participant, the investigator, or study research team. In resolution to a deviation, corrective/preventative actions are to be developed and implemented in a timely manner. Protocol deviations will be documented and reported as required and assessed where necessary during analysis.

8 ASSESSMENT OF SAFETY

The safety of research participants is foremost and should always be considered throughout the conduct of research.

8.1 Definitions

8.1.1 Adverse Events

An adverse event (AE) means any untoward medical occurrence in a patient or clinical investigation participant administered a pharmaceutical product and which does not necessarily have to have a causal relationship with this treatment, and includes an adverse drug reaction (ADR).

An AE can therefore be any unfavorable and unintended sign (including an abnormal laboratory finding, for example), symptom, or disease temporally associated with the use of a medicinal product, whether or not considered related to the medicinal product.

